9.3. Adverse Events

Investigators are responsible for monitoring the safety of subjects who have entered this study and for alerting Lilly or its designee to any event that seems unusual, even if this event may be considered an unanticipated benefit to the subject.

The investigator is responsible for the appropriate medical care of subjects during the study.

Investigators must document their review of each laboratory safety report.

The investigator remains responsible for following, through an appropriate health care option, AEs that are serious or otherwise medically important, considered related to the investigational product or the study, or that caused the subject to discontinue the investigational product before completing the study. The subject should be followed until the event resolves, stabilizes with appropriate diagnostic evaluation, or is reasonably explained. The frequency of follow-up evaluations of the AE is left to the discretion of the investigator.

Lack of drug effect is not an AE in clinical studies, because the purpose of the clinical study is to establish treatment effect.

After the ICF is signed, study site personnel will record via electronic case report form (eCRF) the occurrence and nature of each subject's preexisting conditions, including clinically significant signs and symptoms of the disease under treatment in the study. In addition, site personnel will record any change in the condition(s) and any new conditions as AEs. Investigators should record their assessment of the potential relatedness of each AE to protocol procedure, investigational product, via eCRF.

The investigator will interpret and document whether or not an AE has a reasonable possibility of being related to study treatment, study device, or a study procedure, taking into account the disease, concomitant treatment or pathologies.

A “reasonable possibility” means that there is a cause and effect relationship between the investigational product, study device and/or study procedure and the AE.

The investigator answers yes/no when making this assessment.

Planned surgeries and nonsurgical interventions should not be reported as AEs unless the underlying medical condition has worsened during the course of the study.

If a subject’s investigational product is discontinued as a result of an AE, study site personnel must report this to Lilly or its designee via eCRF, clarifying if possible, the circumstances leading to any dosage modifications, or discontinuations of treatment.

9.3.1. Serious Adverse Events

An SAE is any AE from this study that results in one of the following outcomes:

- death
- initial or prolonged inpatient hospitalization
- a life-threatening experience (that is, immediate risk of dying)
- persistent or significant disability/incapacity
- congenital anomaly/birth defect
- important medical events that may not be immediately life-threatening or result in death or hospitalization but may jeopardize the patient or may require intervention to prevent one of the other outcomes listed in the definition above. Examples of such medical events include allergic bronchospasm requiring intensive treatment in an emergency room or at home, blood dyscrasias or convulsions that do not result in inpatient hospitalization, or the development of drug dependency or drug abuse.

Although all AEs occurring after signing the ICF are recorded in the eCRF, SAE reporting begins after the subject has signed the ICF and has received investigational product. However, if an SAE occurs after signing the ICF, but prior to receiving investigational product, it needs to be reported ONLY if it is considered reasonably possibly related to study procedure.

Study site personnel must alert Lilly or its designee of any SAE within 24 hours of investigator awareness of the event via a sponsor-approved method. If alerts are issued via telephone, they are to be immediately followed with official notification on study-specific SAE forms. This 24-hour notification requirement refers to the initial SAE information and all follow-up SAE information.

Pregnancy (during maternal or paternal exposure to investigational product) does not meet the definition of an AE. However, to fulfill regulatory requirements any pregnancy should be reported following the SAE process to collect data on the outcome for both mother and fetus.

Investigators are not obligated to actively seek AEs or SAEs in subjects once they have discontinued and/or completed the study (the subject summary CRF has been completed). However, if the investigator learns of any SAE, including a death, at any time after a subject has been discharged from the study, and he/she considers the event reasonably possibly related to the study treatment or study participation, the investigator must promptly notify Lilly.

9.3.1.1. Suspected Unexpected Serious Adverse Reactions

Suspected unexpected serious adverse reactions (SUSARs) are serious events that are not listed in the IB and that the investigator identifies as related to investigational product or procedure. United States 21 CFR 312.32 and European Union Clinical Trial Directive 2001/20/EC and the associated detailed guidances or national regulatory requirements in participating countries require the reporting of SUSARs. Lilly has procedures that will be followed for the recording and expedited reporting of SUSARs that are consistent with global regulations and the associated detailed guidances.

9.3.2. Complaint Handling

Lilly collects product complaints on investigational products and drug delivery systems used in clinical studies in order to ensure the safety of study participants, monitor quality, and to facilitate process and product improvements.

Subject will be instructed to contact the investigator as soon as possible if he or she has a complaint or problem with the investigational product so that the situation can be assessed.

9.4. Treatment of Overdose

In case of suspected overdose, hematology, chemistry, vital signs, and oxygen saturation should be monitored and supportive care provided as necessary. There is no known antidote for LY3074828.

9.5. Safety

9.5.1. Electrocardiograms

For each subject, ECGs should be collected according to the Schedule of Activities (Section 2). Electrocardiograms should be recorded according to the study-specific recommendations included in the Schedule of Activities.

Any clinically significant findings from ECGs that result in a diagnosis and that occur after the subject receives the first dose of the investigational treatment should be reported to Lilly or its designee as an AE via eCRF.

9.5.2. Vital Signs

For each subject, vital signs measurements should be conducted according to the Schedule of Activities (Section 2).

Any clinically significant findings from vital signs measurement that result in a diagnosis and that occur after the subject receives the first dose of study treatment should be reported to Lilly or its designee as an AE via eCRF.

9.5.3. Laboratory Tests

For each subject, laboratory tests detailed in [Appendix 2](#) should be conducted according to the Schedule of Activities (Section 2).

Any clinically significant findings from laboratory tests that result in a diagnosis and that occur after the subject receives the first dose of investigational product should be reported to Lilly or its designee as an AE via eCRF.

9.5.4. Other Tests

9.5.4.1. Chest Radiography and Tuberculosis Testing

Posterior-anterior view chest radiography (CXR) will be obtained at screening (Visit 1) (unless local standards dictate posterior–anterior and lateral views), unless the radiographs or medical report from chest radiography performed within 3 months before initial screening (per local standard of care for TB evaluation) are available to the investigator for review.

In addition, subjects will be tested as indicated in the Schedule of Activities for evidence of active or latent TB. A positive TB test result is indicated by a purified protein derivative (PPD) skin test response ≥ 5 mm induration documented 48 to 72 hours after test application (regardless of Bacillus Calmette-Guerin vaccination history). In countries where the QuantiFERON-TB Gold test (or equivalent, for example, T-SPOT) is available and is preferred (in the judgment of the investigator) as an alternative to the PPD skin test for the evaluation of TB infection in a subject, that test may be used instead of the PPD test. Retesting following a positive test is allowed in patients, who in the opinion of the investigator, are unlikely to be infected with *Mycobacterium tuberculosis*. In this circumstance, 2 positive tests is considered evidence of active or latent TB infection. Patients in whom retesting has been performed must be discussed with the medical monitor prior to inclusion in the study.

If the QuantiFERON-TB Gold test is indeterminate, 1 retest is allowed. If the retest is indeterminate, then the subject is excluded from the study.

Subjects with documentation of negative TB test results within 3 months before initial screening may not need to repeat TB testing at screening (Visit 1) based on judgment of the investigator. Documentation of this previous test result must include a record of the size (in millimeters) of the induration response. A PPD test recorded as “negative” without documenting the size of induration (in millimeters) will not be acceptable and will require a retest.

However, subjects with a PPD skin test response ≥ 5 mm induration or a positive QuantiFERON-TB Gold test result at screening and no other evidence of active TB may be rescreened once and enrolled according to the following requirements:

- after receiving at least 4 weeks of appropriate ongoing prophylactic therapy for latent TB as per local standard of care
- no evidence of treatment hepatotoxicity (ALT and AST levels must remain $\leq 2 \times \text{ULN}$) upon retesting of serum ALT and AST levels before randomization)

Such subjects must continue and complete appropriate latent TB therapy during the course of the study to remain eligible and must continue to meet all other inclusion and exclusion criteria for participation.

Subjects who have a documented history of completing an appropriate TB prophylaxis regimen with no history of re-exposure since their treatments were completed and no evidence of active TB are eligible to participate in the study; these subjects should not undergo PPD testing.

Subjects who have had household contact with a person with active TB must be excluded unless appropriate and documented prophylaxis for TB has been given, as described above.

Subjects with any history of **active** TB are excluded from the study, regardless of previous or current TB treatments.

9.5.5. Safety Monitoring

Lilly will periodically review evolving aggregate safety data within the study by appropriate methods.

If a study patient/subject experiences elevated ALT $\geq 3 \times \text{ULN}$, ALP $\geq 2 \times \text{ULN}$, or elevated TBL $\geq 2 \times \text{ULN}$, clinical and laboratory monitoring should be initiated by the investigator. Details for hepatic monitoring depend upon the severity and persistence of observed laboratory test abnormalities. To ensure patient/subject safety and comply with regulatory guidance, the investigator is to consult with the Lilly CRP regarding collection of specific recommended clinical information and follow-up laboratory tests (see [Appendix 4](#)).

Any enrolled subject who is HBcAb+ will undergo periodic monitoring of HBV deoxyribonucleic acid (DNA) per the Schedule of Activities.

In addition to the above, any enrolled subject who is HBcAb+ or tests positive for hepatitis B surface antibody and who experiences an elevated ALT or AST level $> 3 \times \text{ULN}$ must undergo HBV DNA testing. If the HBV PCR test is negative, the investigator should consult with the Lilly-designated medical monitor regarding further management of the subject.

If the result of any HBV PCR test is positive at any time, the subject must be discontinued from the study and should receive appropriate follow -up medical care, including consideration for antiviral therapy. A specialist physician in the care of patients with hepatitis (for example, infectious disease or hepatologist subspecialists) should be consulted and potentially start antiviral therapy.

In the event that safety monitoring uncovers an issue that needs to be addressed by unblinding at the group level, only members of the data monitoring board (an advisory group for this study

formed to protect the integrity of data; refer Section 10.3.7, Interim Analyses) can conduct additional analyses of the safety data.

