Abbreviations: BMC = bowel movement count; BP = blood pressure; C diff = *Clostridium difficile*; CBC = complete blood count; CDAI = Crohn’s Disease Activity Index; **CCI**; CXR = chest X-ray; DNA = deoxyribonucleic acid; ECG = electrocardiogram; ET = Early Termination; FACIT-Fatigue = Functional Assessment of Chronic Illness Therapy–Fatigue; FSH = follicle-stimulating hormone; HBcAb = anti-hepatitis B core antibody; HBsAb = hepatitis B surface antibody; HBsAg = hepatitis B surface antigen; HBV = hepatitis B virus; HCV = hepatitis C virus; HIV = human immunodeficiency virus; hsCRP = high-sensitivity C-reactive protein; HR = heart rate; IBDQ = Inflammatory Bowel Disease Questionnaire; **CCI**; **CCI** NRS = Numeric Rating Scale; PCR = polymerase chain reaction; PK = pharmacokinetic; PGRC = Patient’s Global Rating of Change; PGRS = Patient’s Global Rating of Severity; PPD = purified protein derivative; Q = Question; QIDS-SR16 = Quick Inventory of Depressive Symptomatology–Self Report (16 Items); RNA = ribonucleic acid; SES-CD = Simple Endoscopic Score for Crohn’s Disease; SF-36 = Medical Outcomes Study 36-Item Short Form Health Survey; temp. = temperature; TB = tuberculosis; UV = unscheduled visit; V = visit.

- a Subjects who discontinue early (before V804) should have all of the V804 procedures completed at the last visit attended.
- b At V3 and V5, collect a hematology sample for CBC only, do not collect serum chemistries. Complete blood count is also collected at all unscheduled visits.
- c Use this visit for patients who are seen by the investigator or site staff at a time point not required by the protocol (i.e., an unscheduled visit) due to disease exacerbation or an adverse event. Procedures or laboratory tests may be performed at unscheduled visits at the discretion of the investigator.
- d Stool samples should not be collected on days of bowel prep or endoscopy/colonoscopy. The stool samples may be collected up to 3 days before bowel prep at Visits 7 and 18.

3. Introduction

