8.1. Discontinuation from Study Treatment

8.1.1. *Permanent Discontinuation from Study Treatment*

Discontinuation of the investigational product for abnormal liver tests should be considered by the investigator when a subject meets one of the following conditions after consultation with the Lilly designated medical monitor:

- ALT or AST >8xULN
- ALT or AST >5xULN for more than 2 weeks
- ALT or AST >3xULN and TBL >2xULN or prothrombin time >1.5xULN
- ALT or AST >3xULN with the appearance of fatigue, nausea, vomiting, right upper-quadrant pain or tenderness, fever, rash, and/or eosinophilia (>5%)
- ALP >3xULN
- ALP >2.5xULN and TBL >2xULN
- ALP >2.5xULN with the appearance of fatigue, nausea, vomiting, right quadrant pain or tenderness, fever, rash, and/or eosinophilia (>5%).

Subjects may discontinue treatment for any of the reasons noted above, or for other reasons such as the development of a serious adverse event. To better communicate patient flow throughout the study, different study period situations are provided below:

- Subjects who discontinue the investigational product in Period 1 or Period 2 may continue in the study according to the visit schedule (Section 2).
- At Week 52/Visit 18, subjects who have previously discontinued the investigational product will continue to Visit 801 of the Follow-up Period.
- Subjects who discontinue the investigational product in Period 3 may continue in Period 3 and then proceed to Week 104/Visit 801 of the Follow-up Period.

Investigational product is to be discontinued for patients who experience clinically significant systemic hypersensitivity events (such as anaphylaxis) following administration of investigational product.

8.1.2. *Discontinuation of Inadvertently Enrolled Subjects*

If the sponsor or investigator identify a subject who did not meet enrollment criteria and was inadvertently enrolled, a discussion must occur between the sponsor CRP and the investigator to determine if the subject may continue in the study. If both agree it is medically appropriate to continue, the investigator must obtain documented approval from the sponsor CRP to allow the inadvertently enrolled subject to continue in the study with or without treatment with investigational product.

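### The general hepatic-monitoring trigger in Protocol 9.5.5 omits AST, so an isolated AST rise that does not yet meet an 8.1.1 criterion carries no instruction to start monitoring and consult

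*Protocol*

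**What the plan says.** Protocol 9.5.5 (Safety Monitoring) has a general trigger with three entries: ALT at least 3x ULN, ALP at least 2x ULN, or total bilirubin (TBL) at least 2x ULN. When one is met, "clinical and laboratory monitoring should be initiated by the investigator", and "the investigator is to consult with the Lilly CRP regarding collection of specific recommended clinical information and follow-up laboratory tests", with reference to Appendix 4.

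AST appears in 9.5.5 only in the hepatitis B rule. That rule covers a subject positive for hepatitis B core or surface antibody "who experiences an elevated ALT or AST level" above 3x ULN. Such a subject must have HBV DNA testing. If the result is negative, "the investigator should consult with the Lilly-designated medical monitor regarding further management of the subject"; if it is positive, the subject leaves the study.

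Protocol 8.1.1 lists seven liver conditions under which the investigator should consider stopping study drug, after consulting the sponsor's medical monitor. Four concern transaminases, for example "ALT or AST >5xULN for more than 2 weeks", and all four name ALT or AST. The other three concern ALP.

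**The concern.** The protocol asks the investigator to consider stopping on AST, but the general instruction that starts closer follow-up does not respond to AST. The same laboratory pattern is therefore handled differently depending on which transaminase is raised. An isolated ALT of 4x ULN starts monitoring and a call to the sponsor physician. An isolated AST of 4x ULN does not, unless the hepatitis B rule or an 8.1.1 condition happens to apply.

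What is at stake is early, uniform follow-up of a possible liver signal. It is a matter of subject safety and consistent site action, not of efficacy inference.

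**Working it through.** No power, sample-size or error-rate arithmetic applies. The check sets the rules side by side, counts the entries, and then asks which AST elevations no rule covers.

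**Step 1: count the entries.**

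| Place | Entries | Entries naming AST |
|---|---|---|
| Protocol 9.5.5, general trigger | 3 (ALT, ALP, TBL) | 0 |
| Protocol 8.1.1, transaminase conditions | 4 | 4 |
| Protocol 8.1.1, ALP conditions | 3 | 0 |
| Protocol 9.5.5, hepatitis B rule | 1 | 1 |

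**Step 2: look for AST elsewhere.** AST stands beside ALT in inclusion criterion 11 (both at most 2x ULN), and in SAP 6.14.8.1 in the tables at 3x, 5x and 10x ULN and the subject profiles at 5x ULN or more. It is in the routine chemistry panel (Appendix 2) and the hepatic follow-up panel (Appendix 4). None of these tells the site to start monitoring on an AST value. The SAP items are analyses, and Appendix 4 gives no numeric AST threshold.

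**Step 3: remove the AST rises that are already covered.**

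| AST at least 3x ULN, together with | What the protocol directs |
|---|---|
| ALT at least 3x, ALP at least 2x or TBL at least 2x ULN | 9.5.5 monitoring and consultation, through the other analyte |
| Any 8.1.1 condition met (e.g. AST above 8x ULN, or above 3x with the listed symptoms or eosinophilia) | Consider stopping, with medical-monitor consultation |
| Hepatitis B core or surface antibody positive, AST above 3x ULN | HBV DNA test, then consultation if negative or discontinuation from the study if positive |
| None of the above | No specific instruction |

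**Step 4: describe the last row.** This is a subject negative for both hepatitis B antibodies, with AST at least 3x ULN, ALT below 3x, ALP below 2x and TBL below 2x, and no 8.1.1 condition yet met. Three general provisions still apply:
- Protocol 9.3: investigators document review of each laboratory report, alert the sponsor to anything unusual, and follow medically important adverse events at a frequency that they choose.
- Schedule of Activities: unscheduled chemistry panels are allowed at the investigator's discretion.
- Appendix 4: selected tests may be obtained for a treatment-emergent hepatic abnormality.

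**Step 5: compare with ALT.** For the same subject with ALT in place of AST, 9.5.5 directs monitoring and consultation at 3x ULN. That instruction is the whole difference.

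**The case against.** The strongest reply is that an ALT-led trigger may be deliberate, that the protocol already reacts to AST where it matters, and that the rest is preference. Much of this stands. The SAP's liver plot uses ALT and bilirubin only, which fits an ALT-led approach. The 8.1.1 consultation covers AST once a condition is met. The investigator duties in 9.3 are real, and the sponsor reviews safety data during the study under a plan that is not among the documents. Sections 9.5.5 and 8.1.1 can both be followed as written, so there is no contradiction. None of this, however, supplies an instruction for the last row of the table, and the protocol gives no reason for treating the two transaminases differently there.

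Three stronger readings are tempting and are not supported.

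- **A measurable delay.** A reader might infer that "ALT or AST >5xULN for more than 2 weeks" would be established late for AST, because scheduled chemistries are about four weeks apart in most of the study and the schedule notes say "At V3 and V5, collect a hematology sample for CBC only, do not collect serum chemistries". That spacing comes from the visit schedule. Section 9.5.5 fixes no repeat date for ALT either, so no day count can be assigned to the missing AST entry.
- **An exposed latent-TB group.** Protocol 9.5.4.1 requires "no evidence of treatment hepatotoxicity (ALT and AST levels must remain" at most 2x ULN) before randomization, and "Such subjects must continue and complete appropriate latent TB therapy during the course of the study". A reader might infer that AST is then ignored in these subjects. The same sentence goes on to require that they keep meeting all other eligibility criteria. Criterion 11 caps AST at 2x ULN, so on a plain reading they carry a stricter continuing condition.
- **A missing prothrombin time.** One 8.1.1 condition uses it, but the Appendix 4 tests are optional whichever analyte raises the alarm. This does not separate AST from ALT.

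**Conclusion.** The point holds in a narrow form: early monitoring and sponsor consultation are directed for an isolated ALT rise of at least 3x ULN, but not for an isolated AST rise of that size that falls short of 8.1.1 in a subject outside the hepatitis B rule. It would be wrong to conclude that the protocol has no response to AST, or that the omission is a proven error.

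The number of subjects concerned is unknown. The documents give no frequency for this pattern and none is estimated here. That it is probably very small is a judgment, based on how many conditions must hold together. No endpoint, population or planned analysis changes. The conclusion rests on the protocol and SAP alone; the separate safety-review plan could contain an AST rule that is not visible here.

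**What to change.** In Protocol 9.5.5, change the general trigger to: ALT or AST ≥3x ULN, ALP ≥2x ULN, or TBL ≥2x ULN. Nothing else needs to change.

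The cost is two added words and a few extra follow-up tests and consultations. AST is already in the routine chemistry panel, so detection needs no new sampling. Some triggers will reflect AST of non-hepatic origin; the creatine phosphokinase in the same panel helps to identify those. This is a cheap improvement, not a necessary correction.
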